3. Audiotapes of post-test counseling phone calls will occasionally be recorded for the purposes of supervising test counselors.
4. Clinic records verifying service use will also be used to corroborate participants' reports about appointments attended, services, sought/conducted, and results/lab values from HIV/STI tests conducted.

**B.5.1.1. Custom study web/mobile applications.** Custom web and mobile applications have been developed specifically for this work with data safety and participant confidentiality in mind. Both elements have been used in this project's pilot phase (see Section 3A.5.), but will be further refined during the proposed project's start-up phase to meet the specific needs of this project. While the institutions involved in this research do not constitute 'covered entities' under HIPAA, guidance on data security issues provided through HIPAA/HITECH policies, workgroups, and

work statements provide useful guidance for ensuring the security of health-related data that is collected, stored, and transmitted using web-based tools. As such, we will ensure that all components are developed to comply with these requirements (including the HIPAA Security Rule) for electronic protected health information and other health data. The web and mobile applications will be part of a complex web-based architecture in which all staging components (onboarding web app, participant-side web portal, administrator portal, and mobile app) interact with a centrally-hosted database. The web application will be used to collect self-report and registration data during the screening process (contact, login information). Registration data (current contact information and preferences) can be updated by participants at any time throughout the study by logging in to the secure web portal or the mobile app (for eTEST condition participants). An admin panel of the web application will also be used by study test counselors to log data from post-test counseling phone calls, including testing date, time, and results, referral information provided. The mobile application will be used to collect and relay sensor and device data, user preferences, to provide interactive information about prevention services (e.g., HIV testing, HBST, STI testing, safe sex, PrEP). Both applications are currently hosted locally (on Brown University's servers), ensuring that they are protected by Brown's strict security policies. These policies include server-specific firewalls, restricted access through a virtual private network, IP-specific verification, and encryption (both at rest and in transit). These servers are maintained by IT staff that also provide regular, secure backups, and control physical access via badge entry and sign-in with video surveillance. Together, these specifications ensure that only essential research staff have access to the data that are collected and stored by these tools.

**B.5.1.2. Online self-report questionnaires.** Online questionnaires will be used to collect self-report data as part of the baseline and quarterly follow-up assessments. These questionnaires will be developed and hosted using Qualtrics, which is a web application that affords custom development of web-based surveys. Qualtrics allows strict password protection and limited survey access which ensures that only essential research personnel at the study site will have access to the study data. For these reasons and others, Qualtrics can be used to collect many types of sensitive data, including 21 CFR Part 11, FISMA, and HIPAA data. Surveys can also be mobile-optimized within Qualtrics, allowing study participants to complete surveys on a variety of devices. Qualtrics is currently used by our research team.

**B.5.1.3. Audiotapes of post-test counseling phone calls.** Phone calls between test counselors and eTEST condition participants will occasionally be recorded for the purposes of conducting supervision with test counselors. These tapes will be collected using electronic recording equipment and will be stored in digital files on Brown University's servers. However, they will be stored only until the next supervision meeting (weekly) and will be deleted immediately afterward.

**B.5.1.4. Clinic records verifying service use.** We will also review the records of area clinics to compare with self-report data for each of the proposed outcomes (e.g., HIV testing, STI testing, PrEP consultation, receipt of a PrEP prescription). To facilitate this, participants will be asked to sign and return a HIPAA release in the case that they tested outside of the site clinics. The study informed consent process will also specifically ask participants to consent to allowing us to release limited personal information that reveals their participation in the study to the clinics they

identify for the purposes of verifying service receipt and collecting limited clinical data (e.g., HIV/STI test results, and if positive, CD4 counts and viral loads). Quarterly online surveys will ask participants to name the specific clinics where they received each of the services that the questionnaires inquire about, and site-specific RAs will then request records from these clinics for these participants. Site-specific RAs will download participant data to explore service utilization and compile lists of participants who noted receiving services at each clinic. RAs will then contact each clinic that a participant utilized for HIV/STD testing. Once clinic data is received, site-specific RAs will code it using participants' unique study ID numbers and store it in password-protected files on Brown University's secure servers.

We realize that not all services will be verifiable (e.g., anonymous HIV testing), and that some participants may not be comfortable signing broad releases for their medical information. We also acknowledge that requiring the release of personal medical data may serve as a barrier to enrolling for some participants. At the same time, we also believe it is important to collect more objective data that can serve as a compliment to self-report whenever possible. Given these considerations, returning a signed release will not be required in order to enroll in the study, to prevent this procedure from acting as an impediment to enrollment. Instead, we will verify clinical service information for those who return their releases and consent to this specific procedure. This approach will allow us to verify as much clinical service data as possible, while minimizing participant discomfort with the study's procedures. While this likely means that data on clinical service use will be incomplete, we do not believe that incorporating this procedure undermines the importance of self-report data or the study as a whole. (See Section B4 for a full list of data collected from clinics.)

\*Data Use Agreements will be put in place to allow staff at each study site access to the study database (saved on Brown's servers) in order to verify service use and enter data collected.

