### **Clinic-based HIV/STI testing.**

At the end of the 12-month study period, all participants in all conditions will be asked to present to designated clinics for in-person HIV testing in exchange for a bonus payment (\$50). Encouraging participants in this way can help ensure that we have at least one accurate HIV test result for each (since some may elect not to test at all during the study period, regardless of condition). Results will allow us to more confidently estimate the number of new infections that were successfully detected or missed with HBST versus clinic-based testing reminders. For those who test positive, basic data from the sample (e.g., viral load, CD4 count at the time of confirmatory testing) will be collected from the medical records of each participant, provided they have signed a release. These data will permit us to estimate the "time since infection" for each participant diagnosed with HIV, allowing us to address our exploratory hypothesis that HBST could facilitate earlier diagnosis compared with encouraging clinic-based testing alone.

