### **Clinic records.**

We will also review clinical data for each participant to compare with self-report data on HIV testing, STI testing, and PrEP uptake. We will obtain a signed HIPAA release to review the records of area clinics where participants reported receiving these services. Data on verified service use will be compared across conditions to explore potential differences. While we realize that this data may be incomplete (especially given that some may elect to test at certain sites anonymously), we believe that collecting as much corroborating data as possible will serve as an important compliment to self-report data. Data collected is limited to:

- Date of HIV test
- Viral load
- CD4 cell count
- Type of HIV test (blood vs. antibody)
- HIV status
- Whether the patient received counseling to reduce their risk for HIV
- Date of each STD test
- STD tested
- Test results
- Whether the patient spoke to a provider about PrEP
- Whether the patient was prescribed PrEP

\*Data Use Agreements will be put in place to allow staff at each study site access to the study database (saved on Brown's servers) in order to verify service use and enter data collected.

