Interested participants will be provided with contact information for the local clinical sites where PrEP is provided. During subsequent phone calls, HIV counselors will re-assess PrEP interest and provide additional information upon request. Those indicating interest in PrEP at a prior call will be asked whether they made an appointment, initiated PrEP, and have attended follow-up appointments, which will be corroborated by reviewing medical records.

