## Planned Analyses

Analyses will be conducted in Year 5. To evaluate Aim 1(a), we will use factorial logistic regression to test whether rates of having completed any HIV test over the 12 month study period (assessed via self-report and/or clinic records) differ by study condition. Condition, study site (and their interaction) and other relevant covariates will be entered as predictors, allowing us to explore whether each condition's effects differ by study site. To explore the effects of study condition on regular HIV testing, we will use a generalized estimating equation (GEE) for repeated, binary outcomes, specifying whether participants tested during each 3-month study period as the focal outcome. A logit link function and independent correlation structure will be specified, with study condition, site, and relevant covariates as predictors, to test whether the odds of testing differ across time period, condition, and site. GEEs are a fitting approach for studies in which correlations between repeated measures variables are to be controlled, rather than a central focus of the analysis. For all models of **HIV testing** outcomes, a covariate reflecting whether a given participant had initiated PrEP (and when, for longitudinal models) will be added to each model, since these individuals are required to test for HIV quarterly as a part of ongoing PrEP care. Doing so will allow us to estimate the effects of study arm on HIV testing among those who did not initiate PrEP. Given that we have proposed collecting 54 more participants per site (162 total) than is required to estimate our most complex model (see Model 1b in Section 3C.3.10), we believe we will be fully powered to test this model, even with a high rate of PrEP adoption. While contamination of the control group in our pilot study was rare (only one control participant reported using a HBST), we will also track **where** each participant tested (at home, in person) in quarterly surveys. If contamination is significant, we will employ methods aimed at reducing this bias, including adding indicators of contamination as covariates or bootstrapping. To evaluate Aim 1(b), we will generate variables reflecting whether participants received testing for other STIs or risk reduction counseling during each of the four 3-month intervals of the study period. Similar GEE models will be estimated for these outcomes with time period, condition, and site as predictors, to test whether the odds of receiving each service differ across these factors. To evaluate Aim 2, we will code variables indicating whether participant reports or clinic records reflect participants having consulted with a medical provider about PrEP and/or received a PrEP prescription any time across the study period. Factorial logistic regression with study site, condition, and their interaction will be entered as predictors of this outcome, to test whether the odds of having received consultation and/or a PrEP prescription differ across each of the study sites and conditions. Overall, data from those who drop out or withdraw from the study will be used in these analyses, in intent-to-treat (ITT) fashion. Similarly, we will assume values of zero for all outcomes (i.e., non-receipt of testing or services) when quarterly assessments are missing but participants are retained in the study. Depending on the degree of missing assessments, we will use multiple imputation for these values, since data from missing assessments will likely be missing not at random.

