Additional study-specific training will involve principles of conducting phone-based counseling, role plays, and direct observation through recorded counseling sessions, as well as clinic-based testing conducted at Lifespan (supervised by [name]). Drs. [name] and [name] will also provide ongoing supervision to phone counselors throughout the study. Importantly, all follow-up calls will follow the CDC's guidelines for HIV counseling, testing, and referral, and as such, will involve similar post-test counseling procedures that are currently provided by paraprofessionals and service providers in clinic- and community-based settings worldwide. Participants who test positive with HBST (those in either the standard HBST or eTEST conditions) will be assured that an initially reactive result is not a confirmed positive result. Counselors will then assist participants in scheduling an appointment for confirmatory testing with specific designated clinics at each study site (**Miriam STD/HIV Clinic** or **Fenway Health** in Boston, MA/Providence, RI; **OpenArms** in Jackson, MS; or **AHF Wellness Center** in Los Angles, CA) via three-way calling while participants are on the line. Each of these centers/clinics has standard procedures for providing newly diagnosed patients ongoing HIV care. Site PIs maintain professional affiliations with each, so that site-specific research staff can ensure/confirm whether each participant successfully made their appointments. Test counselors will conduct follow-up calls after each participant's scheduled appointments to ensure that they receive confirmatory testing. Participants with reactive test results will also be screened for suicidality during these calls, and if necessary, intervention will be provided according to National Suicide Prevention Lifeline procedures.

For each study metro area, "primary referral" sites have been designated that provide comprehensive HIV/STI prevention and care services. Each of these sites also provides HIV/STI testing services on a walk-in basis, for free. Study staff and counselors will recommend these clinics to participants first, particularly for confirmatory testing and care for any who receive reactive tests while on the study. These clinics will also serve as the primary site of referral for clinic-based tests they are to receive at the end of their study period.

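### The clinic-record sections conflict on who is asked for a HIPAA release and which clinics are contacted, so the exploratory comparison of verified services is open to differential ascertainment by arm

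*Combined protocol and SAP*

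**What the plan says.** Four places in the combined protocol and SAP govern clinic records.

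- **B.4, Clinic records.** A signed release is to be obtained for area clinics where the man reports HIV testing, STI testing or PrEP uptake. It is not conditional on where he tested. The use is stated: "Data on verified service use will be compared across conditions to explore potential differences".
- **B.4, Clinic-based HIV/STI testing.** For men who test positive, viral load and CD4 count come from medical records, "provided they have signed a release".
- **B.5.1.4, trigger.** Records are to be checked for each proposed outcome, and PrEP consultation and prescription are named. Yet "participants will be asked to sign and return a HIPAA release in the case that they tested outside of the site clinics".
- **B.5.1.4, contact step.** Surveys ask men to "name the specific clinics where they received each of the services that the questionnaires inquire about", and records are then requested from those clinics. Two sentences later the step reads "RAs will then contact each clinic that a participant utilized for HIV/STD testing". Verification is limited to men who return a release and consent to it. A release is not required for enrolment, and the section accepts that the data will be incomplete.

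Two other sections bear on the point. Planned Analyses scores Aim 2 on whether "participant reports or clinic records reflect participants having consulted with a medical provider about PrEP" or received a prescription, and Aim 1(a) on self-report and/or records. The quarterly surveys (B.4) collect the PrEP provider's details in every arm.

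**The concern.** Clinic records are the protocol's objective complement to self-report, and verified service use is to be compared between arms. That comparison is fair only if a service of a given kind has the same chance of being verified in each arm.

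The plan does not secure this. The release is requested after randomisation, because of something the man did or reported. The arms are handled differently in ways that could alter where men seek care and whether they return a form. eTEST men get a counselor call after each detected opening, and on those calls "Interested participants will be provided with contact information for the local clinical sites where PrEP is provided". Standard HBST men get a printed list and controls a texted link. The protocol concedes incompleteness but does not discuss imbalance between arms.

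Research assistants in three metro areas also cannot follow both versions of the text. If sites read it differently, PrEP verification will differ by site for reasons unrelated to the intervention.

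**Working it through.** There is no stated figure to reproduce, because the documents give no verification or release-return rate. The check is a comparison of texts, followed by an illustration with assumed rates.

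**Step 1: the rules side by side**

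| Question | Narrow text | Broad text |
|---|---|---|
| Who is asked for a release? | B.5.1.4: men who tested outside the site clinics | B.4 Clinic records: men reporting HIV testing, STI testing or PrEP uptake at an area clinic |
| Which clinics are contacted? | B.5.1.4, later sentence: those used for HIV/STD testing | B.5.1.4, earlier sentence: those named for any surveyed service |
| Is a release needed for verification or lab data? | B.5.1.4: not requested from men who use only site clinics | B.4 Clinic-based testing and B.5.1.4: needed, no exception for site clinics |

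**Step 2: the narrow text taken literally**

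- A man tests by kit or at a site clinic and gets PrEP from an outside provider. He is not asked for a release and that provider is not contacted, so an Aim 2 event cannot be verified.
- A man uses only site clinics. He is never asked for the release on which CD4 and viral-load collection depends. B.5 makes these clinics the primary referral for the exit test, and counselors schedule confirmatory tests there. The exploratory analysis expects only about 20 diagnoses (6 per group), so each lost case matters.

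**Step 3: either text.** Verification needs a reported service and a returned release. Both arise after randomisation.

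**Step 4: illustration for the verified-only comparison.** Assumed: equal allocation (2000/3, about 667 per arm), no true difference, two-sided 5% test. A and B are any two arms.

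Verified rate = true rate × [site share × site verification + (1 − site share) × outside verification].

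With true rate 15%, site verification 90%, outside verification 20%, site share 60% in A and 40% in B:

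- A: 0.15 × (0.6 × 0.9 + 0.4 × 0.2) = 0.093
- B: 0.15 × (0.4 × 0.9 + 0.6 × 0.2) = 0.072

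Rejection probability = Φ((d − 1.96·s0)/s1) plus the far tail, where d is the difference, s0 = √(2p̄(1−p̄)/n) and s1 = √(pA(1−pA)/n + pB(1−pB)/n). Here d = 0.021, s0 = 0.0151 and s1 = 0.0151, which gives 29%.

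The grid uses true rates of 10, 15 and 25%, site shares of 50/40, 60/40 and 70/30, and outside verification of 10, 20 and 40%. Its ends are:

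- 0.10 × (0.5 × 0.9 + 0.5 × 0.4) = 0.065 v 0.10 × (0.4 × 0.9 + 0.6 × 0.4) = 0.060: 7%
- 0.25 × (0.7 × 0.9 + 0.3 × 0.1) = 0.165 v 0.25 × (0.3 × 0.9 + 0.7 × 0.1) = 0.085: 99%

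Setting overall verification directly, with a 10% true rate and 666 per arm:

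| Verification A / B | Verified A v B | Spurious RR | Chance of p<0.05 |
|---|---|---|---|
| 80% / 40% | 8.0% v 4.0% | 2.0 | 87% |
| 60% / 30% | 6.0% v 3.0% | 2.0 | 75% |
| 40% / 60% | 4.0% v 6.0% | 0.67 | 39% |
| equal | equal | 1.0 | 5% |

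A real effect is distorted too. The pilot PrEP consultation rates, 25% eTEST v 4% control, give RR 6.25. Verified, this becomes 6.25 × 80/40 = 12.5 or 6.25 × 40/60 = 4.2.

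**Step 5: the planned rule.** Event rate = p × [1 − (1 − s)(1 − v)], where s is self-report sensitivity and v is verification. With p = 10% and no true difference:

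- s = 80%, v = 80/40: 0.096 v 0.088, RR 1.09, difference 0.8 points
- s = 95%, v = 60/30: 0.098 v 0.0965, RR 1.02

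The other combinations of s (80, 90, 95%) and v (60/30, 80/40) lie between these. They are upper bounds, because records are sought mainly from clinics the man has already named.

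**The case against.** The strongest reply is that this is a wording inconsistency in an exploratory component. The broad sentences do reach PrEP care and the surveys collect the PrEP provider in all arms, so a missed PrEP record follows from one reading and is not a settled feature of the plan. That stands.

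A reader might infer that the scheme favours eTEST. The documents do not support a direction:

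- The primary clinics are recommended to participants generally: "Study staff and counselors will recommend these clinics to participants first, particularly for confirmatory testing and care". They are free and walk-in for all.
- The locator listing other clinics is in the app, which only eTEST men have. That could raise their outside use.
- The PrEP sites named on calls are not said to be the site clinics.
- If PrEP-only providers are missed, the arm with more PrEP uptake loses more verified events. In the pilot that was eTEST.
- If a release is strictly required, users of site clinics could be the unverified group.

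It can also be said that the release may already be offered at enrolment. B.5.1.4 says consent will ask permission to disclose participation to named clinics, and that a release is not required to enrol. The consent pages are not in the public copy, so this cannot be checked. Permission to disclose participation is not itself a HIPAA release, however, and the stated trigger is a later event.

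Finally, B.5.1.4 weighs men's discomfort with broad releases. That is a fair reason to keep the release optional, but it does not explain why the sections give different rules.

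**Conclusion.** The contradiction is established from the text and needs no assumption: the sections disagree on who is asked for a release, which clinics are contacted, and whether users of site clinics need one. It also follows from the text that verification depends on post-randomisation behaviour.

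That verification will differ between arms is plausible but not shown. Its direction is unknown and every rate in the illustration is assumed. The 29% and the 7% to 99% range show only that the verified-only comparison can mislead badly if verification is unequal; they are not forecasts.

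A reader might also infer that Aims 1(a) and 2 are compromised. They are not, to any important degree: an unverified self-report still counts, and the spurious risk ratio is 1.02 to 1.09 at most under the assumptions used. The exposure lies in the exploratory verified-service comparison and the CD4/viral-load data. This is a worthwhile, inexpensive correction and not a threat to the main results.

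**What to change.** 1. Reconcile B.4 (Clinic records; Clinic-based HIV/STI testing) and B.5.1.4 so that they state one rule.
2. Offer the same optional release to every participant during online consent, before randomisation. It should cover HIV testing, STI testing, risk reduction counseling, and PrEP consultation and prescription, at site and non-site clinics. Enrolment stays unconditional.
3. Have research assistants request records from every clinic named for any of these services, with the same procedure in all arms.
4. Report by arm and by service how many men signed and what share of self-reported services was verified.
5. Run the verified-service comparison among men who signed at consent, a set fixed before randomisation. Label it open to differential ascertainment, since naming a clinic in a survey and the clinic's reply still come later.

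The cost is consent-screen and procedure wording and some extra record requests, mostly to PrEP-only providers. A few men who would have signed later may decline up front, and restricting the comparison to signers makes it smaller. The Aim 1 and Aim 2 outcome definitions need no change.
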